primary hypotheses with at least 80% power at two-sided alpha level of 0.05. In particular, with 53 subjects per group we have 87% power to detect a treatment by time interaction of magnitude $f=0.24$ and 80% power to detect pairwise differences of magnitude $d=0.6$ or higher at two-sided alpha level of 0.05. Holm-Bonferroni adjustment will be used for the pairwise comparisons and is taken into account in the power calculation so that the family-wise error rate for the pairwise comparisons is kept at 0.05 level. Testing of between group differences over time will be performed within the mixed effects models which are expected to be even more powerful since they use all available data on each individual including data on subjects who dropout or have intermittent missing data due to non-compliance with the treatment schedule. To address potential limitations related to the external validity, we have expanded the age range (18-70), included active duty military personnel and non-OEF/OIF/OND Veterans, and will use stratified randomization to match and balance on study site and alcohol use comorbidity during the trial. Additionally, we plan to track participant duty status, years since trauma and treatment history, and examine these factors in post-hoc analyses.

Analysis plan: Descriptive statistics will be calculated prior to statistical analysis. Distributions of quantitative variables will be assessed for normality using normal probability plots and Kolmogorov-Smirnov statistics and transformations or non-parametric methods will be used as necessary. All statistical tests will be two-sided. Uncorrected alpha level of 0.05 will be used for testing the primary hypothesis as described below. Pairwise post-hoc comparisons and tests of secondary outcome measures will be adjusted using Holm-Bonferroni procedure. Randomized treatment groups will be compared at baseline on potentially confounding factors (e.g. age, sex, history of substance abuse) and variables that are significantly different between groups will be included as additional covariates in the models below. All analyses will be intent-to-treat.

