Primary specific aim: To test the dose-related effects of ketamine on PTSD symptoms in Veterans and active duty military population. We will follow our prior PTSD clinical trial,⁵ using mixed effects regression models, with group, time, group by time effects for the primary outcome variable (PCL-5). We will stratify by infusion center and alcohol use comorbidity. We do not expect to observe significant differences in treatment effects by infusion center but we will test the interaction of treatment group and infusion center and perform follow-up analyses by site as necessary. Similarly, we do not expect significant moderating effects of alcohol use comorbidity but will assess the interaction between treatment and alcohol use comorbidity and perform follow-up tests as necessary. This approach will be applied to most secondary outcome measures as well. Mixed effects regression models use all available data on each subject, are flexible in modeling the correlation structure of the data and give unbiased results under missing at random assumptions. We will select the best-fitting correlation structure for the primary and each secondary outcome based on Schwarz-Bayesian Information Criterion (BIC). Time will be considered as a categorical predictor and post-hoc tests between groups will be conducted for the change from baseline to end-point, which is of primary interest. To assess the trajectory of ketamine effects over time, we will test for linear, quadratic and higher order time trend differences. Post-hoc tests will also be performed to assess whether dose effects are linear. Change in PTSD symptoms is expected to be the largest for the higher dose ketamine group. However, it is possible that the change in the higher dose ketamine group is not significantly different from the change in the lower dose ketamine group. Thus, we will also estimate effect sizes with confidence intervals for the change from baseline to end-point in each group and use this information together with safety data to inform dose selection for potential future studies of ketamine efficacy and evaluation of mechanism of action in PTSD.

In addition to testing the potential moderating effect of comorbid alcohol use described above, we will also perform exploratory analyses to assess moderating effects of depression, medication

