## Supplemental

Mixed models were constructed to evaluate the effects of posttraumatic stress disorder (PTSD) treatment on the PTSD Checklist for DSM-5 (PCL-5), Clinician-Administered PTSD Scale for DSM-5, Montgomery-Asberg Depression Rating Scale (MADRS), Clinician-Administered Dissociative State Scale (CADSS), and Positive and Negative Syndrome Scale (PANSS) based on all available observations within individual patients. Treatment group (Standard, Low, Placebo), time (pre each infusion, 24 hours post-first and post-last infusions for PCL-5 and MADRS, baseline and post-last infusion for CAPS-5, during each session for CADSS and PANSS), site and all possible interactions were fit as fixed effects. Alcohol use disorder (AUD) diagnosis was included as a covariate. The CADSS and PANSS models also included interval (30 and 120 minutes) and the interaction between interval and treatment. Subject was the clustering factor. The best-fitting variance-covariance structure in each model was selected based on Bayesian information criterion. Residuals were assessed, and CADSS was logtransformed to correct for positive skewness of this outcome. In the final models, nonsignificant interactions not involving treatment were dropped for parsimony. Focused least square mean comparisons of change from baseline to 24 hours post-first infusion and from baseline to 24 hours post-last infusion within treatment group, and for pairwise differences in change from baseline between treatment groups, were evaluated regardless of the significance of the interactions and main effects. Follow-up data on the PCL-5 and CAPS-5 also were analyzed using mixed models covarying for baseline severity. Individuals with open label treatment were excluded from these analyses. Responder status was calculated as at least 25% improvement from pretreatment on the PCL-5. Missing data were treated as failure (i.e., nonresponder). The primary analyses for the binary outcomes were logistic regressions with treatment, site, and AUD as predictors, and missing treated as failure. The treatment by site interactions were nonsignificant and were dropped for parsimony in the final models.

For the PCL-5 self-assessments, 1.6% of assessments specified incorrect index trauma event referenced for symptom scoring, and 23.6% of assessments were completed without specifying the index trauma. A sensitivity analysis determined that mixed methods ANOVA results were essentially unchanged with or without their inclusion.

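### Beyond site and alcohol use disorder, covariates are chosen by baseline significance tests, which leaves the model undefined in advance and gives up precision

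*Protocol*

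**What the plan says.** The protocol's Analysis plan paragraph (under Statistical Consideration, section IV.F) sets the rule in two steps. First, "Randomized treatment groups will be compared at baseline on potentially confounding factors (e.g. age, sex, history of substance abuse", and so on; the list is given by example only. Second, "variables that are significantly different between groups will be included as additional covariates in the models below". It does not say which test or significance level decides, or whether a selected variable enters as a main effect or with a time interaction.

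Two factors are outside this rule. In the Primary specific aim paragraph the protocol says "We will stratify by infusion center and alcohol use comorbidity". In the SAP (Supplemental), "site and all possible interactions were fit as fixed effects" alongside treatment and time, and "Alcohol use disorder (AUD) diagnosis was included as a covariate". No time interaction is mentioned for AUD. The SAP also drops interactions that do not involve treatment when they are nonsignificant.

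The primary analysis is specified as "using mixed effects regression models, with group, time, group by time effects for the primary outcome variable (PCL-5"), with time categorical, and "post-hoc tests between groups will be conducted for the change from baseline to end-point, which is of primary interest". The logistic model for remission (protocol) controls for site and alcohol comorbidity. The SAP's logistic models for the binary outcomes use treatment, site and AUD. The SAP text names no covariate chosen by baseline testing, and does not say whether the protocol's rule was applied or dropped.

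**The concern.** Under randomisation, a significant baseline difference is a chance event. Its p-value measures the size of the imbalance relative to noise. It does not measure whether the variable predicts PCL-5 change. The rule can therefore bring in variables that do not matter and leave out strong predictors whose imbalance is modest. Most of the gain from covariate adjustment comes from explaining outcome variance in every trial, not from reacting to the occasional large imbalance, and this rule gives that gain up.

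The rule also leaves the primary model, the secondary mixed models and the logistic models undefined until baseline data by arm have been examined, and someone then has to choose the test, the cut-off and the functional form. For the primary contrast the form decides whether the adjustment has any effect.

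**Working it through.** **The plan's own figure.** Inputs from Sample size justification: 53 per group, d = 0.6, two-sided tests, Holm-Bonferroni allowed for. Pairwise power = Φ(d√(n/2) − z), with d√(n/2) = 0.6 × √26.5 = 3.089.
- Alpha 0.025: Φ(3.089 − 2.241) = 80.2% (79.1% with the t distribution). The stated 80% reproduces at this level.
- Alpha 0.05/3, the first Holm step for three comparisons: 75.6% (t: 74.3%).
- Alpha 0.05, no multiplicity adjustment: 87.0% (t: 86.4%). This is the reference for the comparison of strategies below.

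The stated 87% for the interaction cannot be checked, because the number of time points and the correlation are not given. It does not bear on this point.

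**How often the rule is triggered.** The screening level is not stated. The protocol gives "Uncorrected alpha level of 0.05 will be used for testing the primary hypothesis as described below", and I assume the same level for screening, with k independent tests. P(at least one enters) = 1 − 0.95^k.
- k = 3 (the named examples): 14.3%
- k = 5: 22.6%
- k = 10: 40.1%

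The number of candidates is not given. With dependent tests, the probability for k = 3 can lie anywhere from 5% (complete dependence) to 3 × 0.05 = 15%.

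**Type I error and power.** Three-arm analysis of covariance on change, 53 per arm, two-sided 0.05 for one pairwise comparison; 40,000 simulated null trials and 20,000 at d = 0.6. The correlation ρ between covariate and change is not in the documents, so a range is shown.

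| Assumed ρ | Type I error, screening | Type I error, always adjusted | Power, screening | Power, always adjusted |
|---|---|---|---|---|
| 0.3 | 4.7% | 4.9% | 86.5% | 89.2% |
| 0.5 | 4.7% | 5.2% | 87.7% | 94.4% |
| 0.7 | 4.0% | 4.8% | 88.0% | 99.0% |

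An analytic check agrees. The standard error of the adjusted difference is √(2(1 − ρ²)/53). At ρ = 0.5 this is 0.168, and Φ(0.6/0.168 − 1.96) is about 94.6%. In the null simulation at ρ = 0.5 the SD of the estimate was 0.169 when always adjusted and 0.191 under screening. A given covariate is flagged in only about 5% of trials, so about 95% are analysed unadjusted for it.

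**What a selected covariate does to the primary contrast.** Suppose E(Y) = μ(group, visit) + γx, with baseline as one of the repeated outcomes and γ constant over visits. With complete data and saturated group-by-visit means, the fitted mean for a cell is the raw mean minus γ times the arm's mean of x. That correction is the same at baseline and end-point, so it cancels from the change. A generalised least squares fit to simulated data shows this. The true effect on change was 0, the arms differed by 0.534 in x, and x had a slope of −4 on change, so the expected bias was −4 × 0.534 = −2.137.
- No covariate: −2.540 (SE 0.757)
- Covariate as main effect: −2.540 (SE 0.757)
- Covariate by time: −0.317 (SE 0.778)

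Dropout barely changes this. In a simulation with 10 visits, 66 per arm and 20% dropout, the main effect moved the contrast by 0.003 to 0.008 SD on average, and the covariate-by-time term by about 0.09 SD.

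**Binary outcomes.** A logistic model has no baseline term to cancel against, so an added covariate can change the treatment odds ratio. The documents give no basis for sizing this.

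**The case against.** The best defence has four parts.

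1. *The models already have fixed covariates.* This is correct. A reader might infer that nothing enters unless it fails a baseline test, but site and AUD enter regardless and the follow-up models always carry a severity covariate. The criticism is confined to additional covariates.
2. *The rule can do its job.* This is also correct, depending on the form. In a model of change at ρ = 0.5, type I error among flagged trials is 14.5% unadjusted and 4.9% adjusted. A reader might infer that the rule never corrects imbalance. The documents do not support that, because they do not fix the form. There are hints of a main effect: AUD is called simply a covariate where site is given interactions, and nonsignificant interactions not involving treatment are dropped. These are hints only.
3. *No false-positive risk is created.* This stands. Selection uses baseline data, not outcomes, and is written down beforehand. A shifted odds ratio after adjustment is not in itself bias.
4. *The SAP shows that the rule added nothing.* It lists the fitted terms in the past tense, with no covariate selected at baseline, so this is a plausible reading. It remains an inference from silence, since the SAP does not mention the rule. Equally, nothing supports the inference that a reported result was altered by it.

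The 40% figure assumes ten independent tests; the named examples give 14%. Either is a probability of triggering, not a measure of harm.

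**Conclusion.** The point holds as a flaw in covariate selection. The protocol lets chance imbalance decide which further covariates enter, from an open list and in an unstated form, and the SAP does not settle whether that happened. There is no inflation of type I error: 4.0% to 4.7% in simulation for ρ from 0.3 to 0.7.

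The loss is in precision and definition. In a change-score model, pre-specified adjustment gains 2.7, 6.7 and 11.0 percentage points of power over screening at ρ = 0.3, 0.5 and 0.7. These differences rest on an assumed ρ, one prognostic covariate, a screening level of 0.05 and a comparison at unadjusted 0.05. If no strong predictor of change exists, the gain is small. For a time-constant main effect, the absence of any correction to the change contrast is exact with complete data and close to exact with 20% dropout. The stronger claim of no protection under any form is not supported.

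**What to change.** - Delete the baseline-significance rule from the protocol's Analysis plan, and do not use baseline tests to select covariates.
- In the PCL-5 model, keep site-by-time and add AUD-by-time. Retain both whatever their significance, as an exception to the SAP's practice of dropping nonsignificant interactions that do not involve treatment.
- Name any further prognostic covariates in advance, each with its time interaction.
- Add baseline severity to the remission and response logistic models.
- Reconcile the severity covariate in the follow-up models: Exploratory aim 2 in the protocol uses severity at the end of treatment, while the SAP uses pretreatment (Brief Statistical Analysis Plan) or baseline (Supplemental) severity.
- State in the SAP whether the rule was applied, which variables were tested, and whether any covariate entered because of it. As the SAP is written in the past tense, any of these terms added now should be labelled as added after the analysis.

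The cost is a few sentences, a few degrees of freedom and the loss of after-the-fact flexibility.

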Primary specific aim: *To test the dose-related effects of ketamine on PTSD symptoms in the Veteran and active duty military populations.* In this 2-site study, approximately 198 eligible Veterans and active duty personnel who meet criteria for PTSD and the additional inclusion and exclusion criteria (detailed in Section III-A) will be randomized to one of three treatment arms (placebo, ketamine 0.2 mg/kg, ketamine 0.5 mg/kg). Participants will receive the study drug or placebo via intravenous infusion twice per week for 4 weeks. The primary outcome measure will be the PTSD Checklist (PCL-5). Data will be stratified by site (Texas vs. Connecticut) and by the presence of comorbid mild-to-moderate alcohol dependence. A random effects/mixed model will be applied to the data. The study is powered based on the effect size of ketamine in the Mount Sinai study to detect a significant interaction of ketamine dose and time during this trial.

Secondary specific aims:

1. Safety of repeated ketamine exposure: We will evaluate the safety of ketamine exposure in the following ways: (1) induction and persistence of psychotic and dissociative symptoms will be evaluated during ketamine infusion, prior to discharge at each ketamine test day, and at two weeks and one month following the last ketamine infusion; (2) breath alcohol levels will be evaluated prior to randomization, throughout the trial, and for 4 weeks following the last ketamine exposure; (3) medical and psychiatric adverse events and serious adverse events will be recorded following FDA, VA Cooperative Studies Program, and Consortium for the Alleviation of PTSD (CAP) guidelines.

2. Durability of benefit: Following completion of the randomized testing, psychometric ratings (PCL-5 and other outcome measures) and safety assessments will be obtained on a weekly basis for 4 weeks to qualitatively and quantitatively characterize (random effects model covarying for end-of-treatment severity) the dose-related durability of benefit in responders to the randomized treatment.

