study evaluating the effectiveness of a single infusion of ketamine (one dose, 0.5 mg/kg) has been studied in 22 PTSD patients in comparison to 19 PTSD patients who were administered midazolam at Mount Sinai.²⁷ The present revised study builds upon the pilot data from the Mount Sinai study to address many of the limitations of its study design: 1) Sample size – The proposed study is much larger and likely to yield definitive results, 2) Dose – The proposed study would compare two doses of ketamine (0.2 mg/kg, 0.5 mg/kg), 3) Inactive comparator – This study would incorporate placebo as a reference for evaluating ketamine effect, 4) Study population – The prior study was conducted in a civilian population while the proposed study would recruit active duty personnel, Veterans who served in combat following 9/11, and other Veterans, 5) Outcome measure – the prior study employed the Impact of Events Scale as the primary outcome measure, while the proposed study would employ the PTSD Checklist-5 (which yields score highly correlated with CAPS-5 but with reduced respondent burden), and 6) Number of ketamine infusions – We propose 8 ketamine infusions over 4 weeks followed by a 4-week follow-up making this trial the length of many standard PTSD studies. Thus this study is a critical bridge between the initial observation in PTSD and the development of NMDA receptor antagonist administration as a treatment for PTSD. A significant result ($p \leq 0.05$, two-tailed) for our primary analysis would serve as the basis for a “go decision” and continued research and development of ketamine as a viable treatment alternative for PTSD. It would also justify the exploration of more highly experimental subtypes and selective NMDA receptor antagonists (ifenprodil, Glyx-13, AZD-6765, CP101, 606, etc.) for the treatment of PTSD.

IV. RESEARCH PLAN:

This study is being conducted as part of the Consortium To Alleviate PTSD (CAP) and is proposed as a 2-site, 3-arm randomized, double-blind, controlled clinical trial to test the safety and efficacy of repeated doses of ketamine as compared to placebo, in reducing symptoms of Posttraumatic Stress Disorder (PTSD) in an active duty military and Veteran population.

A. Subjects:

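### Does the plan leave open which PCL-5 test decides the primary question, and does the end-point contrast need promoting?

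*Protocol*

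**What the plan says.** **Protocol, Significance.** A two-tailed p of 0.05 or less "for our primary analysis would serve as the basis for a" go decision on further development. The sentence names no model term, contrast or visit.

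**Protocol, Primary specific aim.** The trial is powered "to detect a significant interaction of ketamine dose and time during this trial".

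**Protocol, Sample size justification.** With 53 per group the trial is sized for its "primary hypotheses with at least 80% power at two-sided alpha level of 0.05". Two figures follow: 87% power for the interaction at f = 0.24, and 80% for pairwise differences at d = 0.6. For the second, "Holm-Bonferroni adjustment will be used for the pairwise comparisons and is taken into account in the power calculation".

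**Protocol, Analysis plan.** "Uncorrected alpha level of 0.05 will be used for testing the primary hypothesis as described below"; pairwise post-hoc comparisons and secondary outcomes get Holm. Time is categorical, and "post-hoc tests between groups will be conducted for the change from baseline to end-point, which is of primary interest". In addition, "we will test for linear, quadratic and higher order time trend differences". Effect sizes with confidence intervals for change to end-point are planned in each group, to "use this information together with safety data to inform dose selection for potential future studies of ketamine efficacy".

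**SAP.** The Brief Statistical Analysis Plan lists all three model effects as the primary analysis and places the comparisons 24 hours after the first and last infusions under secondary analyses. The Supplemental section evaluates those comparisons whatever the interaction shows.

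**The concern.** No sentence says outright that the group-by-time interaction is the test behind the go statement. The sample size section speaks of primary hypotheses in the plural; the analysis plan gives uncorrected 0.05 to one. The contrast with a direction and a time, the change to end-point, is ranked post-hoc in one document and secondary in the other, and the Protocol's analysis plan attaches no visit to it.

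The interaction, taken alone, is an omnibus test. With three arms and ten PCL-5 times it has (3 − 1)(10 − 1) = 18 df, no sign and no visit. It can be significant because of an early difference that has gone by the end of treatment, and it can miss a late one. If either the interaction or an end-point contrast could be claimed as the primary result, error control would also suffer.

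**Working it through.** **1. Which term?** Three statements point the same way. The aim names the dose-by-time interaction as the powered effect. The sample size section derives a single overall effect size for it. The uncorrected 0.05 can belong only to that test, because the pairwise tests are assigned to Holm.

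The effect sizes agree. The protocol takes d = 0.8 for 0.5 mg/kg against placebo and d = 0.6 against 0.2 mg/kg, so the arms lie at 0, 0.2 and 0.8. Their SD (divisor 3) is 0.340, and 0.340/√2 = 0.240, the stated f.

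**2. The plan's own power figures.**
- Pairwise: 0.6 × √(53/2) = 3.089. At two-sided alpha 0.05/2 the critical value is 2.241, so power is Φ(0.847) = 0.80. Simulating the three-pair Holm procedure with arms 0/0.2/0.8 gives 0.80 for 0.5 against 0.2 mg/kg and 0.96 for 0.5 mg/kg against placebo. The stated 80% reproduces.
- Interaction: the 87% cannot be reproduced uniquely, because the number of times and the correlation behind it are not given. A 2-df F test with λ = 0.24² × 159 = 9.16 gives 77%; with 198 patients it gives 86%; standard repeated-measures versions give 97% or more. It cannot be called wrong.

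**3. Which visit?** Under Dependent Measures, the CAPS-5 is taken at end of treatment; Table 2 puts that CAPS-5 at Visit 11, Day 25. Day 28 is the optional open-label visit. The last PCL-5 time in the SAP's treatment-phase model is 24 hours after the last infusion. Day 25 is the natural reading.

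**4. Would a Day 25 rule do better?** The comparison rule is: ketamine better than placebo at Day 25, at either dose, after three-pair Holm. Inputs are 53 per arm, arms 0/0.2/0.8, and Days 0, 1, 3, 7, 10, 14, 17, 21, 24 and 25. Effects are in SDs of change from baseline at each visit. Four covariance structures are assumed, each with total variance 1:
- compound symmetry, correlation 0.5;
- autoregressive, 0.7 per week;
- random intercept 0.5 plus autoregressive 0.5 (0.9 per day);
- random intercept 0.5 plus autoregressive 0.3 (0.9 per day) plus noise 0.2.

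The noncentrality is λ = n × Σ(aᵢ − ā)² × m′W⁻¹m. Here a = (0, 0.25, 1), m is the 0.5 mg/kg profile of nine changes, and W is their covariance. The first factors give 53 × 0.5417 = 28.71. For a sustained d = 0.8 under compound symmetry, m′W⁻¹m = 0.64 × 9/(1 + 8 × 0.5) = 1.152, so λ = 33.1. Power from the noncentral F with 18 and 156 (159 − 3) or 1404 (156 × 9) df is 95.5% or 97.0%.

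| Assumed profile, 0.5 mg/kg against placebo | 18-df interaction | Day 25 Holm rule |
|---|---|---|
| d = 0.8 from Day 1 to Day 25 | 95.5–98.2% | 96% |
| Linear rise to d = 0.8 at Day 25 | 73–99.8% | 96% |
| d = 0.8 on Day 1, half on Day 3, zero from Day 7 | 78–99% | about 1.7% |

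In the first row, trials where Holm succeeds and the interaction does not cannot exceed 100 − 95.5 = 4.5%. In the second row such trials reach about 19% under the two autoregressive structures with 1404 df, and about 24% with 156 df. Even there, the planned linear-trend difference (2 df) is significant in 97% or more.

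**The case for a change.** The strongest case for a change is that inferring the interaction does not give it a direction or a time. The third row of the table is real: a significant interaction can coexist with no benefit at Day 25. The loss in the second row is also real if benefit accrues slowly and correlation decays with time. Finally, if success meant the interaction or any Holm-adjusted end-point contrast, simulated null rejection rises from 4.9% to 8.2% (assumed correlation 0.5).

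All of this stands as arithmetic, but its reach is limited. The 8.2% arises only if someone counts either result as the primary success, whereas the plan gives the uncorrected alpha to one hypothesis and treats the pairs as a separate post-hoc family. The early-only profile assumes that the effect vanishes by Day 7 while infusions continue; the Ketamine regimen justification chose the schedule expecting the response to be held. A slow ramp from zero likewise sits badly with the 24-hour onset in the Background. An early effect that fades would also be a finding of interest, since rapid action is one of the protocol's stated motives; a Day 25 rule would count it as failure.

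Misreading the direction is not a practical risk. The go sentence concerns development of ketamine as a viable treatment, and the adjusted contrasts and effect-size intervals show the sign.

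**Conclusion.** The labels conflict: one contrast is called the main interest, post-hoc and secondary in different places, and the interaction is never named outright as the deciding test. That is missing detail which an analyst following both documents fills in one sensible way: interaction first at 0.05, then Holm-adjusted changes to 24 hours after the last infusion, read with their direction and intervals. The go statement is a sentence of rationale, not a formal decision rule.

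Replacing the omnibus test with a Day 25 contrast is a design preference. It gains essentially nothing under a rapid, sustained effect (about 96% against 95.5–98.2%). It gains up to about 23 points under a slow ramp (96% − 73%) and gives up an early effect. The SAP is written in the past tense and reports findings, so moving the success criterion now would be an outcome-aware change that cannot restore pre-specification.

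The power figures rest on the protocol's effect sizes, 53 completers per arm, and assumed covariances and time profiles; they are illustrations. The reading of the term and the visit rests on the text alone. No change to the plan follows.

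### The efficacy figure named for dose selection is the change within each arm; between-arm differences with confidence intervals would answer the dose question better, at no cost

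*Protocol*

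**What the plan says.** The sentence is in the protocol, section IV.F, Statistical Consideration, in the Analysis plan paragraph on the primary specific aim. The paragraph expects the largest change on the higher dose, then allows that "it is possible that the change in the higher dose ketamine group is not significantly different from the change in the lower dose ketamine group". Its answer to that possibility is an added output: "estimate effect sizes with confidence intervals for the change from baseline to end-point in each group and use this information". The stated purpose is to guide, alongside the safety results, which dose any later efficacy studies would use.

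Three other elements bear on the point.

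- The same paragraph makes group, time and group by time the primary model. It plans that "post-hoc tests between groups will be conducted for the change from baseline to end-point, which is of primary interest", and adds: "Post-hoc tests will also be performed to assess whether dose effects are linear".
- The Sample size justification says that "Holm-Bonferroni adjustment will be used for the pairwise comparisons and is taken into account in the power calculation", and states 80% power at d = 0.6 with 53 per group.
- The SAP (Supplemental) evaluates focused comparisons of change within each treatment group and also "for pairwise differences in change from baseline between treatment groups". It has no sentence on dose selection.

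Neither document names a between-arm effect size with a confidence interval as the input to dose selection.

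**The concern.** The primary aim is the dose-related effect, and the protocol's Significance section gives placebo as the reference against which ketamine is to be judged. A change from baseline in one arm is drug effect plus whatever would have happened on saline. Its confidence interval describes the sum, so it cannot show what a dose contributes.

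The sentence is also tied to the case where the direct high-versus-low test was not significant. There the useful quantity is an interval for the difference between doses, because it shows which differences remain compatible with the data. Two separate within-arm intervals do not give that.

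What is at stake is the advice carried into later studies. The protocol's regimen justification expects fewer side effects at the lower dose. A within-arm change that looks convincing, read beside a better safety profile, could make a dose that adds nothing over saline look acceptable.

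**Working it through.** **Inputs from the protocol.** 53 completers per arm (Subjects; Sample size justification); d = 0.6 for high versus low dose; two-sided alpha 0.05; Holm-Bonferroni across the three pairwise comparisons.

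**Assumptions.** Changes are in units of the SD of change, with SD 1 in every arm. The documents give no figure for placebo response, so a shared non-specific change c is taken as 0.2 to 0.6 SD. Each arm's change is treated as one normal variable rather than as output of the full mixed model.

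**Step 1: the plan's own figure.** The standard error of a difference is √(2/53) = 0.194, and 0.6/0.194 = 3.09.

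- At alpha 0.025 (second Holm step): Φ(3.09 − 2.24) = 80.2%.
- At alpha 0.05: Φ(3.09 − 1.96) = 87.0%.
- At alpha 0.05/3: 75.6%.

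The stated 80% with Holm is reproduced.

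**Step 2: interval widths.**

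- Change in one arm: t(52)/√53 = 2.007/7.280 = 0.276 SD.
- Difference between two arms: t(104) × √(2/53) = 1.983 × 0.194 = 0.385 SD.

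**Step 3: a dose equal to saline, all trials.** The chance that its own 95% interval excludes zero comes from the noncentral t with 52 df and noncentrality c√53.

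| Shared change c | Inactive dose's interval excludes zero |
|---|---|
| 0.2 SD | 30% |
| 0.4 SD | 82% |
| 0.6 SD | 99% |

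The saline arm's interval does so equally often.

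**Step 4: the case the sentence addresses.** Simulate three arms with true changes c (placebo), c (low dose) and c + 0.6 (high dose), and apply Holm to the three comparisons. High versus low is non-significant in about 22-23% of trials. Within those trials:

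| Shared change c | Low dose's own 95% interval excludes zero | Saline's own interval excludes zero |
|---|---|---|
| 0.2 SD | about 65% | about 32% |
| 0.4 SD | about 98% | about 83% |
| 0.6 SD | nearly 100% | about 99% |

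In the same trials the unadjusted 95% interval for low minus placebo excludes zero in about 7%, and the Holm-adjusted test is significant in about 3%. The low-dose figures exceed those in Step 3 because a missed high-versus-low difference is more likely when the low arm happens to do well.

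**Step 5: does overlap of separate intervals mislead here?** With equal n and SD, two arms' intervals separate only when the means differ by more than 2 × 0.276 = 0.551 SD. That is 0.551/0.194 = 2.84 standard errors, p about 0.005, below even the strictest Holm step of 0.0167. So when the direct test is non-significant the intervals practically always overlap, and the overlap hides no significant difference.

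**The case against.** The strongest reply is that dose selection does not rest on these figures. They are an additional output, read with safety data, and meant only to inform possible later studies. Beside them stand the Holm-adjusted pairwise tests, including each dose against placebo, and a test of dose linearity. The estimates are for every group, so the saline change is shown next to both doses, and an inactive dose would look much like saline and usually fail its planned comparison. All of this stands and limits the harm.

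Two stronger readings are tempting, and the documents support neither.

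- A reader might infer that an inactive dose would be declared effective because its own interval excludes zero. The plan contains no such rule.
- A reader might infer that the doses would be wrongly judged alike because their intervals overlap. No overlap rule is written either, and Step 5 shows that the argument fails in the very case the sentence addresses.

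Regression to the mean is also weak support. Entry is selected on CAPS-5 at screening, while the outcome is PCL-5 with a baseline before the first infusion, so part of any regression may already have happened. The point needs only placebo response.

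The reply does not remove one gap. Subtracting the saline column by eye gives no interval, and neither document links the pairwise contrasts to dose selection or promises effect sizes with intervals for them.

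**Conclusion.** The point holds as a free improvement. The quantity named as the efficacy input to dose selection is not placebo-controlled and does not measure the difference between doses. Quantities that do both are available from the same fitted model.

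In the illustration, when the high-versus-low test misses a true 0.6 SD difference, the inactive dose's own interval excludes zero in about 65% to nearly 100% of trials, against about 7% for its difference from placebo. These figures rest on 53 per arm, equal SDs, a low dose exactly equal to saline, and an assumed shared change of 0.2 to 0.6 SD. They show how little a within-arm interval says about drug effect. They are not the error rate of any rule in the plan. No efficacy test, error rate or sample size of this trial changes.

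**What to change.** Reword the dose-selection sentence in the protocol's Analysis plan (primary specific aim). Name as the efficacy input the between-arm differences in change from baseline to end-point from the same mixed model, given as effect sizes with confidence intervals:

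- 0.5 mg/kg minus placebo
- 0.2 mg/kg minus placebo
- 0.5 mg/kg minus 0.2 mg/kg

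Keep the within-arm changes, with placebo among them, as description. State whether the intervals are adjusted for multiplicity, so that they can be read beside the Holm-adjusted tests. The SAP already evaluates the pairwise differences, so the cost is wording and one summary table, with no extra patients, visits or data.
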